Participants assigned to receive WASABI will complete at least 3 EMA sessions per week, 1 hour of digitally delivered Cognitive Behavioral Group Therapy (dCBGT) per week, and weekly cognitive biases assessments and self-reports for 12 weeks. During the intervention, these participants will also have daily access to 1:1 and group chat Instant Messaging (IM) and may have weekly electronic check-ins with Site Study personnel (as needed). Participants in the control condition will be asked to attend 1 hour of digitally delivered Cognitive Behavioral Group Therapy (dCBGT) per week for 12 weeks and may have weekly electronic check-ins with Site Study personnel (as needed).

For each arm, as soon as 3-6 participants have completed the baseline assessments and randomization, a cohort will be assembled. The Study Coordinator will meet with the participants to orient them to the study platforms and the WASABI Clinician will meet with each participant individually for a brief introduction and orientation prior to the 12-week intervention and will review of the *Procedures and Guidelines to Group Therapy*. The WASABI Coordinator and/or Clinician will create a virtual support group open only to cohort participants. The WASABI Clinician will explain her role, make group introductions, and will invite participants to attend weekly 1-hour group sessions (dCBGT+ WASABI or dCBGT only, depending on the treatment arm). For the treatment group (dCBGT + WASABI), between group sessions, the WASABI Clinician will spend approximately 30 min/day keeping the chat active during work hours, checking it approximately 3 times a day and may respond to messages participants leave, as appropriate. The WASABI Coordinator will be included in the support group chat and may monitor the chat content, and may be active in the chat in the absence of the WASABI Clinician.

Participants will be re-evaluated again at the expected time of completion, immediately following the 12-week intervention, to evaluate changes in performance. Finally, participants will be asked to fill out an online exit survey to rate enjoyment, usability, perceived benefits, and ease of fit into schedule.

The protocol will be conducted in accordance with the protocol submitted to and approved by the reviewing Institutional Review Board and approval will be obtained prior to implementation.

Study Population

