Experimental Treatment Intervention (dCBGT+WASABI): The Experimental Treatment Intervention is a mobile-delivered and clinically-supervised adjunct to treatment composed of three primary treatment tools. Participants will be asked to 1) attend 12 weekly, 1-hour, group dCBGT sessions and complete "homework" associated with traditional dCBGT; 2) complete 3 EMA sessions per week, weekly standardized SA self-report, and weekly cognitive assessments; 3) use IM for 1:1 and group conversations. At the beginning of each treatment cohort, the WASABI Clinician will create a group text open only to cohort participants, explain their role, and make introductions. Between group sessions, the WASABI Clinician will spend approximately 30 min/day keeping the chat active during work hours, checking it approximately 3 times a day and responding to any messages participants leave, as appropriate. The WASABI Clinician will also receive notifications whenever the WASABI algorithm detects SA symptom exacerbation, and engage participants in synchronous or asynchronous IM. In absence of alerts, the WASABI Clinician will monitor the WASABI dashboard the day before each dCBGT session to customize the delivery of targeted content during the videocall.

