The active control program is designed to: 1) be a face-valid approach to remediation in anxiety disorders, to ensure that participants remain blind to group affiliation, and match the experimental treatment program in halo or expectation-based influence on performance in outcome measures; 2) match the experimental treatment program in overall dCBGT session intensity, time-spent attending, and overall engagement; and 3) provide a comparison group that matches the experimental treatment group on the aforementioned attributes, but without the adjunct to treatment component, WASABI.

To use the active control, a participant opens Google Meet, a HIPAA-compliant videoconferencing and instant messaging application on an Internet-connected iOS mobile device and goes to a general log-in screen. The participant then logs in using a study provided account). Participants assigned to the active control are expected to join 12, 1 hour-long dCBGT sessions using the Google Meet application. These will be scheduled and facilitated by the WASABI Clinician. To complete the BrainHQ embedded assessments, a participant opens a standard application (BrainHQ) on an Internet-connected iOS device and goes to a general log-in screen. The participant then logs into the experimental treatment program platform through the BrainHQ application (using a study provided username that contains no personally identifiable information).

Application Security

BrainHQ: All usage and progress data collected through the BrainHQ application is encrypted then transmitted to a central server. Data is encrypted in transit and at rest, and access is limited and audited. Data collected through the BrainHQ platform will not include geographic information. IP address data is stored only in memory and in request logs, and is used for technical support and troubleshooting, but not persisted with the participant's data. However, data as it relates to dates that assessments are completed is collected and stored. The EMA

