G-Suite Google Chat and Meet: This platform allows participants to communicate with others via the app without having to share their full name, mobile phone number or email to do so. Participants also have the opportunity to personalize their profile, by entering a short bio and a picture of their choice. In order to access the Google Meet and Chat apps, participants will have a unique username/login that contains no personally identifiable information. Once logged in, they will be operating within the Google Meet and Chat HIPAA-compliant digital environment, and data that are produced, transmitted, and shared among users will be exclusively visible/readable to the research participants and authorized University of Minnesota and Posit Science staff. These data will include personally identifiable information—such as faces, first names or aliases, biographical and medical information—similar to what happens during all in-person group therapy sessions. The Google Meet and Chat API will allow participants to exchange end-to-end encrypted instant and group messages, as well as make end-to-end encrypted group voice and video calls. Participants will be aware that research team members at the University of Minnesota and Posit Science will have access to the group chat history and will be monitoring its contents throughout the intervention period. As such, participant are informed that any personally identifying information voluntarily shared on this platform will be viewed by staff at both the University of Minnesota and Posit Science. Google Meet and Chat use end-to-end encryption for voice and video calls, as well as instant messages. Google Meet and Chat's voice calls are encrypted with DTLS and SRTP, its video calls with RTP, and its instant messages with RTP. In addition to this, client-server communication is protected by Transport Layer Security. More information about how Google Meet and Chat protects privacy can be found here: <https://support.google.com/a/answer/3407054>

Participants assigned to the Active Control condition will not be asked to use the Google Chat app, as it is unique to the WASABI intervention. Participants in both groups will be able to download other Google apps associated with their deidentified study assigned G-Suite account, such as Google Calendar and Gmail, to facilitate communication with the Site Study team and

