- Second, individual sessions will be held between the Site Study Coordinator and/or WASABI Clinician and each participant to educate them regarding confidentiality prior to entering the intervention. Participants will be informed that 1) they have the right to choose an alias rather than their first name and decide at any point what information they choose to disclose; 2) the WASABI Clinician will respect the patients' ability to choose what they disclose, and keep the promises of faithfulness and loyalty to all participants, including not revealing information participants disclose; 3) the WASABI Clinician cannot promise that other group members will maintain confidentiality; 4) the WASABI Clinician may have a legal obligation to break confidentiality in certain circumstances (e.g., child abuse), and those circumstances will be fully explained. The WASABI Clinician will follow established procedures appropriate for their local jurisdiction to report such knowledge; 5) the UMN and Posit Science research teams will be monitoring the BrainHQ (EMA questionnaires) and Google Meet and Chat contents, including chat history, throughout the intervention and as such any volunteered information that may be personally identifying will be available to both UMN and Posit Science monitors.

- Third, participants will be asked to read, sign and agree to be bound by a modified version of the American Psychological Association procedures and guidelines for group therapy (<http://www.apadivisions.org/division-49/publications/newsletter/group-psychologist/2011/04/group-procedures.aspx>), adapted for the target population, while in the intervention.
- Finally, during the first group therapy session, the WASABI clinician will encourage group members to embrace the concept of confidentiality, making it their own rather than a mandatory rule.

Given that one of the goals of WASABI is to enhance social functioning in people with social anxiety, we will not discourage group members from sharing contact information and befriending other study participants. Research shows that peer-to-peer interactions occur naturally on social media platforms and serve many purposes, such as establishing new relationships, maintaining relationships, reconnecting with people, disclosing personal experiences of living with social anxiety, seeking and sharing information related to symptoms and medications.

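### The protocol contradicts itself on whether control cohorts get a support group chat, and it states no block on Chat for control accounts

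*Protocol*

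**What the plan says.** The cohort paragraph in the protocol's General Study Design opens: "For each arm, as soon as 3-6 participants have completed the baseline assessments and randomization, a cohort will be assembled". It then states: "The WASABI Coordinator and/or Clinician will create a virtual support group open only to cohort participants". Only after that does it narrow to the treatment group, for the clinician's roughly 30 minutes a day in the chat. It closes with: "The WASABI Coordinator will be included in the support group chat and may monitor the chat content".

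Two other sections assign messaging by arm. Under Experimental Treatment Intervention: "At the beginning of each treatment cohort, the WASABI Clinician will create a group text open only to cohort participants". Under Application Security (G-Suite Google Chat and Meet): "Participants assigned to the Active Control condition will not be asked to use the Google Chat app, as it is unique to the WASABI intervention".

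The Active Control Program section describes the control platform thus: "To use the active control, a participant opens Google Meet, a HIPAA-compliant videoconferencing and instant messaging application". On contact between members, the Confidentiality section says: "we will not discourage group members from sharing contact information and befriending other study participants".

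The SAP (Statistical Plan, Feasibility) analyses group-chat messages per week as a primary engagement outcome in participants randomized to WASABI+dCBGT.

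**The concern.** Messaging is part of what the trial adds to dCBGT. The Experimental Treatment Intervention section lists it as the third of three primary treatment tools. The Background presents peer-to-peer messaging, separately from clinician messaging, as a way to extend support beyond the clinic. The comparator is defined as matching the experimental arm except for WASABI.

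Staff who assemble a control cohort from the General Study Design paragraph could open a peer group for it. The comparator would then hold one element of the add-on, and the incremental difference in secondary outcomes would tend to be pulled towards zero. The Sample Size Justification says that the data from this trial will be used to power the Phase II trial, so a shrunken difference would carry forward.

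**Working it through.** No alpha, power or sample-size figure is involved, so the check is a comparison of the texts.

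**1. Scope of the support-group sentence**

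| Order in the cohort paragraph | Content | Arm |
|---|---|---|
| 1 | Cohort assembled | Each arm |
| 2 | Orientation by coordinator and clinician | Not limited |
| 3 | Virtual support group created | Not limited |
| 4 | Introductions and invitation to weekly sessions | Both arms, named explicitly |
| 5 | Clinician's daily time in the chat | Treatment group only |
| 6 | Coordinator included in the support group chat | Not limited |

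The sentence at step 3 lies between two that cover both arms, and it comes before the first restriction. Read literally, it applies to control cohorts. Step 6 links the support group to a chat, so reading it as only the weekly video call is possible but strained.

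**2. Text that places chat in the WASABI arm only**

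- The preceding paragraph of General Study Design gives WASABI participants daily one-to-one and group messaging. For controls it lists only the weekly session and check-ins as needed.
- The Experimental Treatment Intervention section repeats the group-creation step, but for treatment cohorts.
- The Active Control Program section lists sessions, homework and two sets of embedded assessments. It lists no chat.
- Application Security calls Chat unique to WASABI and names it apart from the other Google apps open to both arms.

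The intent is therefore clear, and the support-group sentence departs from it.

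**3. Is there a stated barrier?** Controls hold a study G-Suite account. Application Security says that they are not asked to use Chat. It does not say that Chat is unavailable to them. The Extra Time item under Description of Protocol Devices says that Meet and Chat may stay available until the final session, with no limit by arm. No section disables Chat for controls or names control-arm use as a deviation.

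**4. What would be recorded?** Application Security, Data Management and Confidentiality all provide for monitoring of chat history by both research teams. The SAP's message count covers the WASABI arm. The protocol's Data Analysis section sets its target of 8 messages a week for that arm only. That section also mentions comparing dCBGT engagement with the control condition, but gives no message count for controls. No item asks either arm about contact outside the study accounts.

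**5. Size.** Access would come by cohort. One control cohort of 3 to 6 is 3/12 = 25% to 6/12 = 50% of the 12 planned controls. If every control cohort were given a group, it would be all of them. This is access, not use or benefit. Proportional shrinkage of the between-arm difference would be *m* × *e*, where *m* is the share of the add-on's effect due to peer messaging and *e* is the fraction of controls who obtain that benefit. The documents give neither value.

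**The case against.** The strongest reply is that this is one loose sentence, outweighed by everything else. Chat access is assigned by arm one paragraph earlier, the control is described at length without it, and Chat is called unique to WASABI. The term virtual support group is undefined and could, for controls, mean only the video group. This stands as to intent. A reader might infer that the plan delivers a core component of the add-on to controls, and the documents do not support that. Even on the literal reading, controls would lack the clinician's daily chat time, EMA, alerts and the dashboard.

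Two of the supporting citations are weak. The matching platform sentence for the WASABI arm names Meet and Chat together, whereas the control sentence drops Chat, so its mention of instant messaging looks like leftover wording. Friendships between members can arise in any group therapy and belong to the comparator as much as to WASABI.

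A reader might also infer that control-arm messaging would go unseen. It would not on study accounts, because chat history is monitored and protocol deviations are reviewed monthly. What is missing is a count by arm and any measure of off-platform contact.

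Finally, the primary outcomes are feasibility measures in the WASABI arm, and the protocol concedes that 24 participants cannot power an augmentation effect. That limits the consequence. It does not remove it, since the secondary difference is carried into Phase II planning.

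**Conclusion.** The concern holds as an internal contradiction and an unstated access control. The support-group sentence in General Study Design cannot be squared as written with the Experimental Treatment Intervention and Application Security sections, and nothing stated would stop a control account from using Chat.

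If the literal reading were followed, the likely direction is a smaller between-arm difference in secondary outcomes. This assumes that peer messaging has some benefit, as the Background proposes, and that controls would use it. Feasibility outcomes in the WASABI arm would be unaffected.

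The amount cannot be derived from the documents. A reader might set messaging at a third to a half of the add-on effect and suppose that half of controls benefit fully, which gives 1/3 × 1/2 = 17% to 1/2 × 1/2 = 25%. Every input there is assumed, so these figures should not be cited as an estimate. Nor do the documents show that any control cohort was given a chat. The correction is worth making because it costs little and protects the contrast that the trial is meant to inform.

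**What to change.** 1. In General Study Design, limit the virtual support group and its chat to dCBGT+WASABI cohorts, in line with Experimental Treatment Intervention and Application Security. Align the Active Control Program's description of Meet.
2. In Application Security, state that Chat is disabled on control-arm study accounts during the intervention and until V3, with Meet, Calendar and Gmail kept.
3. Report study-account message counts by arm.
4. Add one item, in both arms, to the online exit survey (step 8 of Study Procedures) on messaging with group members outside sessions.

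The cost is two wording changes, one account setting, one extra tabulation and one survey item. The limitation is that off-platform contact between controls can only be measured, not prevented.

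The SAP is partly in the past tense and cites a control group of 8, so conduct may be complete. In that case, report by-arm counts from any retained chat history and carry the corrected wording into the Phase II protocol.
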